### **7.3.1 Primary analyses**

#### **Single rising dose parts under fasting and fed conditions**

Analysis of safety and tolerability is described in [Section 7.3.4](#).

### **Food effect part**

The pharmacokinetic endpoints listed in [Section 5.5.1](#) will be calculated according to the BI Standard Operating Procedure (SOP) 'Standards and processes for analyses performed within Clinical Pharmacokinetics/Pharmacodynamics' [[001-MCS-36-472](#)].

Plasma concentration data and parameters of a subject will be included in the statistical pharmacokinetic (PK) analyses, if they are not flagged for exclusion due to a protocol violation relevant to the evaluation of PK (to be decided no later than in the Report Planning Meeting) or due to PK non-evaluability (as revealed during data analysis, based on the criteria specified below). Exclusion of a subject's data will be documented in the CTR.

Relevant protocol violations may be

- Incorrect trial medication taken, i.e. the subject received at least one dose of trial medication the subject was not assigned to.
- Incorrect dose of trial medication taken.
- Use of restricted medications.

Plasma concentrations and/or parameters of a subject will be considered as non-evaluable, if for example

- The subject experienced emesis that occurred at or before two times median  $t_{\max}$  of the respective treatment (median  $t_{\max}$  is to be determined excluding the subjects experiencing emesis).
- The subject experiences emesis at any time during the labelled dosing interval.
- A pre-dose concentration is  $>5\%$  of the  $C_{\max}$  value of that subject.
- Missing samples/concentration data at important phases of PK disposition curve.

The PK parameter analysis set (PKS) includes all subjects in the Treated Set (TS) who provide at least one primary or secondary PK parameter that was not excluded according to the description above. Thus, a subject will be included in the PKS, even if he contributes only one PK parameter value for one period to the statistical assessment. Point estimates of bioavailability, the ratios of the gMeans (test/ reference) for the primary and secondary endpoints (see [Sections 5.5.1.1](#) and [5.5.1.2](#)), and their two-sided 90% confidence intervals (CIs) will be provided.

To this end, the PK endpoints will be log transformed (natural logarithm) prior to fitting the ANOVA model (see [Section 7.1.3](#)). For each endpoint, the difference between the expected means for  $\log(T) - \log(R)$  will be estimated by the difference in the corresponding adjusted means (LeastSquares Means), and a two-sided 90% confidence interval based on the t-distribution will be computed. These quantities will then be back-transformed to the original scale to provide the point estimate and 90% CIs for each endpoint.

### 7.3.2 Secondary analyses

#### **Single rising dose parts under fasting and fed conditions**

The secondary parameters (see [Section 5.5.1](#)) will be calculated according to the BI Standard Operating Procedure (SOP) ‘Standards and processes for analyses performed within Clinical Pharmacokinetics/Pharmacodynamics’ [[001-MCS-36-472](#)]. Analyses will be performed for BI 705564.

Plasma and urine concentration data and parameters of a subject will be included in the statistical pharmacokinetic (PK) analyses, if they are not flagged for exclusion due to a protocol violation relevant to the evaluation of PK (to be decided no later than in the Report Planning Meeting) or due to PK non-evaluability (as revealed during data analysis, based on the criteria specified below). Exclusion of a subject’s data will be documented in the CTR.

For more information on relevant protocol violations and the definition of the PKS, see [Section 7.3.1](#). Excluded subjects will be listed with their individual plasma concentrations. Individual pharmacokinetic parameters, however, will not be included in descriptive statistics for plasma concentrations, pharmacokinetic parameters or other statistical assessment.

#### Assessment of dose proportionality

Dose proportionality will be assessed using the secondary pharmacokinetic endpoints as specified in [Section 5.5.1.2](#). Two separate analyses will be performed, one for the doses under fasting conditions, and one for the doses under fed conditions.

The basic model for the investigation of dose proportionality will be a power model that describes the functional relationship between the dose and PK endpoints.

$$\exp(Y_{ij}) = \alpha' * \exp(X_i)^\beta * \varepsilon'_{ij}$$

The model consists of a regression model applied to log-transformed data. The corresponding ANCOVA model includes the logarithm of the dose as a covariate.

Together with  $\alpha' = \exp(\alpha)$  and  $\varepsilon'_{ij} = \exp(\varepsilon_{ij})$ , taking natural logarithms converts this model to a linear form as follows:

$$Y_{ij} = \alpha + \beta * X_i + \varepsilon_{ij}$$

where

$Y_{ij}$	logarithm of the pharmacokinetic endpoint for subject j at dose level i; j = 1, 2, ..., N;
$\alpha$	intercept parameter;
$\beta$	slope parameter;
$X_i$	logarithm of dose i;
$\varepsilon_{ij}$	random error associated with subject j at dose level i (assumed to be independent and identically normally distributed).

This equation can be fit as a linear regression model.

Based on the estimate for slope parameter ( $\beta$ ), a 2-sided 95% CI for the slope will be computed. Perfect dose proportionality would correspond to a slope of 1. The assumption of a linear relationship between the log-transformed pharmacokinetic endpoint and the log-transformed dose will be checked.

If dose proportionality over the entire dose range investigated cannot be shown, an attempt will be made to identify dose range(s), where dose proportionality can be assumed.

Graphical displays: To support the analyses of dose proportionality, graphical representations of the data might be created. These might include (but are not limited to) individual time-courses of trough plasma concentrations and the gMean plasma concentration time profiles.

### **Food effect part**

The secondary parameters (see [Section 5.5.1](#)) will be calculated according to the BI SOP 'Standards and processes for analyses performed within Clinical Pharmacokinetics/ Pharmacodynamics' [[001-MCS-36-472](#)] and will statistically be assessed using the same methods as described for the primary endpoints.

### **7.3.4 Safety analyses**

Safety will be assessed for the endpoints listed in [Section 5.2.1](#). All treated subjects (i.e., all subjects who received at least one dose of study drug), will be included in the safety analysis. Safety analyses will be descriptive in nature and will be based on BI standards. No hypothesis testing is planned.

The analyses will be done by 'treatment at onset'.

Treatments will be compared in a descriptive way.

In the single rising dose parts, the placebo control group in the safety evaluation will consist of all placebo treated subjects, regardless of the dose group in which they were treated and regardless of whether they participated in the single rising dose part under fed or under fasting conditions; the active treatment groups will be compared to the placebo group in a descriptive way. To explore potential differences between placebo subjects under fasting and under fed conditions, these two subgroups will be compared descriptively.

In all (single rising dose – fasting and fed - and food effect) parts, tabulations of frequencies/proportions will be used for the evaluation of categorical (qualitative) data, and tabulations of descriptive statistics will be used to analyse continuous (quantitative) data.

Measurements (such as ECG, vital signs, or laboratory parameters) or AEs will be assigned to treatments (see [Section 4.1](#)) based on the actual treatment at the planned time of the measurement or on the recorded time of AE onset (concept of treatment emergent AEs).

Therefore, measurements planned or AEs recorded prior to first intake of trial medication will be assigned to 'screening', those between first trial medication intake until the end of trial visit will be assigned to the treatment period. These assignments including the corresponding time intervals will be defined in detail in the TSAP. Please note that AEs occurring after the last per protocol contact but entered before database lock will be reported to drug safety only and will not be captured in the trial database.

Additionally, further treatment intervals (analysing treatments) may be defined in order to provide summary statistics for time intervals, such as combined treatments, on-treatment totals or periods without treatment effects (such as screening and post-study intervals).

Adverse events will be coded using the Medical Dictionary for Regulatory Activities (MedDRA). Frequency, severity and causal relationship of AEs will be tabulated by treatment, system organ class and preferred term. SAEs, AESIs (see [Section 5.2.2.1](#)) and other significant AEs (according to ICH E3) will be listed separately.

Laboratory data will be compared to their reference ranges. Values outside the reference range as well as values defined as clinically relevant will be highlighted in the listings. Additionally, differences from baseline will be evaluated.

Vital signs or other safety-relevant data observed at screening, baseline, during the course of the trial and at the end-of-trial evaluation will be assessed with regard to possible changes compared to findings before start of treatment.

For the single rising dose parts (under fasting and fed conditions) of the study, a centralised evaluation of all 12-lead ECGs recordings (see [Section 5.2.4](#)) will be the basis for the derivation of further ECG parameters based on the ECG variables QT, HR, QTcF, QTcB, PR, QRS, and RR. The baseline value of an ECG variable is defined as the mean of the triple ECG measurements prior to drug administration. The derivation of the quantitative and qualitative ECG endpoints and their analyses will be described in the TSAP.

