FE part: separately for each treatment, ranging from administration time of study drug until administration time of next study drug dose or 0:00 h on the day after trial termination date)

Please note that all AEs reported between start of trial drug administration and the last per-protocol contact will be considered on treatment (i.e. no follow-up period is considered in this trial).

Displays of AEs will be presented separately for the treatments described in [Table 6.1: 1](#) and [Table 6.1: 2](#) above, including “Placebo total”.

Two types of AE displays will be provided in the report:

- A)** Section 15.3 (separately for combined SRD parts and FE part) and Appendix 16.1.13.1.8 (for ClinicalTrials.gov (separately for combined SRD parts and FE part) and EudraCT (all parts combined)) of the CTR displays:

In these displays, the on treatment phase will be analysed (labelled with the name of the study treatment (short label)). Screening will not be included in this analysis.

The following totals will be provided in addition:

- a total over all on treatment phases included in this analysis ("Total on treatment") (Section 15.3 only)
 - SRD parts: a total over all BI-treated phases under fasting conditions (“BI fast total”)
 - SRD parts: a total over all BI treated phases under fed conditions (“BI fed total”)
 - SRD parts: a total over all BI-treated phases (“BI total”)
- B)** Section 15.4 and Appendix 16.1.13.1.8 (except for ClinicalTrials.gov and EudraCT) of the CTR displays:
- Screening

- On treatment (labelled with the name of the study treatment (short label))

In Section 16.1.13.1.8 AE tables (separately for combined SRD parts and FE part), the following totals will be provided in addition:

- a total over all study phases ("**Total**")

Tables of vital signs, ECG and laboratory values will present results by the above mentioned on treatment phase, including "Placebo total".

For detailed information on the handling of the treatments in the O*C views refer to Technical TSAP ADS (analysis data set) plan.

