7. PLANNED ANALYSIS

The combined SRD parts and FE part will be evaluated separately.

In the combined SRD parts, the placebo group under fasting (labelled “Placebo fast”) and the placebo group under fed conditions (labelled “Placebo fed”) will be compared, as well as the combined placebo group (labelled “Placebo total”) to all active treatment groups.

Safety analysis (refer to [Section 7.8](#)) will be performed by _____ and will be presented in Sections 15.1 to 15.4 of the CTR and in Appendix 16.2 and 16.1.13.1.

Inferential statistical analyses of PK endpoints (refer to Sections [7.4](#) and [7.5.2](#)) will also be performed by _____ and will be presented in Section 15.5 of the CTR and in Appendix 16.1.13.3.

Descriptive data analysis of PK parameters and concentrations will be performed by BI and will be presented in Section 15.6 of the CTR.

Descriptive data analysis of PD endpoints will be performed by department Translational Medicine and Clin. Pharmacology at BI and will be presented in Section 15.7 of the CTR.

The format of the listings and tables will follow the standards defined in the BI corporate guideline “Reporting of Clinical Trials and Project Summaries” [001-MCG-159] [\(6\)](#) with the exception of those generated for PK-calculations.

In the combined SRD parts, the individual values of all subjects will be listed, sorted by treatment group, subject number, and visit.

In the FE part, the individual values of all subjects will be listed, sorted by treatment sequence, subject number, visit and actual treatment (if appropriate).

The listings will be included in Appendix 16.2 of the CTR.

For end-of-text tables, the set of summary statistics for non-PK parameters is:

N	number non-missing observations
Mean	arithmetic mean
SD	standard deviation
Min	minimum
Median	median
Max	maximum

For analyte concentrations as well as for all PK parameters, the following descriptive statistics will additionally be calculated:

CV	arithmetic coefficient of variation
gMean	geometric mean
gCV	geometric coefficient of variation

The data format for descriptive statistics of concentrations will be identical with the data format of the respective concentrations. The descriptive statistics of PK parameters will be calculated using the individual values with the number of decimal places as provided by the evaluation program. Then the individual values as well as the descriptive statistics will be reported with three significant digits in the CTR.

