7.8 SAFETY ANALYSIS

All safety analyses will be performed on the TS.

If not stated otherwise, the safety results will be sorted by treatment group (combined SRD parts) or by actual treatment (FE part).

In the combined SRD parts, the placebo group under fasting (labelled “Placebo fast”) and the placebo group under fed conditions (labelled “Placebo fed”) will be analysed separately and compared, as well as the combined placebo group (labelled “Placebo total”) to all active treatment groups.

The safety data for treated subjects who failed to complete the study (dropouts or withdrawals) will be reported as far as their data are available. All withdrawals will be documented and the reason for withdrawal recorded.

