7.8.3 Vital signs

Descriptive statistics over time including change from baseline will be performed for vital signs (blood pressure and pulse rate).

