7.8.4 ECG

Continuous safety ECG monitoring (by investigator) – (SRD parts only)

Clinically relevant abnormal findings will be reported as adverse events.
No separate listing or analysis of continuous ECG monitoring will be prepared.

12-lead ECG (SRD parts + FE part)

Abnormal findings will be reported as baseline conditions (at screening) or as AEs (during the trial) if judged clinically relevant by the investigator.

All evaluations of ECG data will be based on the TS, except the exposure-response analyses, which are based on the ECGPCS set.

The following ECG analyses will only be performed in the SRD parts:

Listing of individual data

For all quantitative endpoints, listings of individual data will be shown in Appendix 16.2. For QTcB and RR only listings will be provided. Occurrences of notable findings will be flagged.

Comments regarding the ECGs will be listed.

Categorical endpoints

For the categorical endpoints, frequency tables will be provided.

For all subjects with any notable finding in ECG intervals, a separate listing will be created as end-of-text display (based on the same display template as in Appendix 16.2), and the corresponding time profiles will be shown.

Quantitative endpoints:

Descriptive statistics (N, mean, SD, min, median, max) will be provided for the changes from baseline over time of QTcF, HR, QT, PR and QRS. The time profiles of mean and SD for the changes from baseline on treatment will be displayed graphically by treatment.

For QTcF and HR changes from baseline the relationship to the corresponding plasma concentration is evaluated using an exposure response model.

This model will be evaluated separately for doses under fasting conditions and doses under fed conditions.

For the following analyses, all time points with available ECG endpoints and time-matched plasma concentrations of all dose groups will be included. For the handling of missing values see [Section 6.6](#).

The response variable will be the change from baseline in QTcF (Δ QTcF). The placebo subjects will be included in the analysis, setting their plasma concentrations to zero.

As a first step, it is investigated if there is a potential delayed or accelerated (e.g. metabolites) effect of the drug on QTcF. A general visual impression is provided by overlaying time profiles of plasma concentrations and QTcF changes from baseline (Δ QTcF). All figures will

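### Does comparing each rising-dose group with placebo pooled over fasted and fed subjects let a breakfast effect pass for a drug effect in the early Day 1 safety tables?

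*Protocol*

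**What the plan says.** Protocol 7.3.4 forms the placebo control for the safety evaluation from all placebo subjects, whether treated "under fed or under fasting conditions; the active treatment groups will be compared to the placebo group in a descriptive way". The next sentence adds a check: "To explore potential differences between placebo subjects under fasting and under fed conditions, these two subgroups will be compared descriptively". The same section also says, more broadly, that treatments are compared descriptively and that no hypothesis is tested.

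SAP Table 6.1: 1 gives separate labels to *Placebo fast*, *Placebo fed* and *Placebo total*. SAP 7 says the first two "will be compared, as well as the combined placebo group" with the active groups. SAP 7.8 goes further: they "will be analysed separately and compared, as well as the combined placebo group" with all active groups. On layout, SAP 6.1 says: "Tables of vital signs, ECG and laboratory values will present results by the above mentioned on treatment phase", with *Placebo total* included. Totals over active groups ("SRD parts: a total over all BI-treated phases", and its fasted and fed subsets) are listed only for the AE displays.

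The measures in question are vital signs (SAP 7.8.3: "Descriptive statistics over time including change from baseline will be performed for vital signs") and ECG intervals (SAP 7.8.4: descriptive statistics "will be provided for the changes from baseline over time of QTcF, HR, QT, PR and QRS").

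**The concern.** The pooled control mixes two meal conditions, while each active dose column has one. In Flow Chart 3 (fed part) the pre-dose ECG and vital signs are planned at -2:00, breakfast at -0:30 and dosing at 0:00. In Flow Chart 1 (fasted part) there is no food before lunch, which follows the 4:00 assessments. By schedule, then, a high-fat meal lies between baseline and the early readings in the fed part only. The 4 h laboratory sample is likewise non-fasted only in the fed part (Protocol 5.2.3).

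The first 4 hours are also when Protocol 2.3.2.7 expects exposure to be highest, and the fed part contains the top dose, 160 mg. Someone who looked only at *Placebo total* could take part of a meal effect on pulse rate or QTcF for a drug effect in fed groups, or miss part of a drug effect in fasted groups.

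**Working it through.** **Inputs.** Six fasted and four fed dose groups of 8, each with 6 active and 2 placebo (Protocol 3.1, Tables 3.1: 1 and 3.1: 2); 12 subjects in the food effect part. The plan's total reproduces: 6×8 + 12 + 4×8 = 92. The documents give no meal effect and no SD for these measures. I write m for the meal effect on change from baseline and assume a common SD.

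**Placebo mix.** Fasted 6×2 = 12, fed 4×2 = 8, total 20: weights 0.6 and 0.4.

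**Carry-over.**
- Fed group minus *Placebo total*: m - 0.4m = +0.6m.
- Fasted group minus *Placebo total*: 0 - 0.4m = -0.4m.
- Either group minus its own placebo column: 0.
- With the two optional fed groups, placebo is 12 + 12 and the terms are ±0.5m.

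These are upper limits. Flow Chart 3, footnote 2, allows pre-dose procedures at any time within 3 h before dosing, and a baseline taken after breakfast would already contain part of m. For assumed heart-rate effects of 2, 5 or 10 bpm, the limits are +1.2, +3 or +6 bpm (fed) and -0.8, -2 or -4 bpm (fasted).

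**Readings affected.** Visit 2 post-dose times up to 4:00 are 0:30, 1:00, 1:30, 2:00, 3:00 and 4:00: 6 of 12 ECG times, 6 of 13 vital-sign times and 1 of 4 laboratory samples.

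**Price of matching.** The SE of a difference for 6 active subjects against n placebo subjects is SD × sqrt(1/6 + 1/n):

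| Placebo column | n | SE |
|---|---|---|
| Total | 20 | 0.465 SD |
| Fast | 12 | 0.500 SD (+7%) |
| Fed | 8 | 0.540 SD (+16%) |

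**Break-even in mean squared error.**
- Fed: (0.6m)² = SD² × (1/8 - 1/20) = 0.075 SD², so m = 0.456 SD.
- Fasted: (0.4m)² = SD² × (1/12 - 1/20) = 0.0333 SD², so again m = 0.456 SD.

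Below that value the pooled column is closer to the truth on average; above it, the matched column is.

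**What the planned check can show.** Fasted versus fed placebo: SE = sqrt(1/12 + 1/8) = 0.456 SD. With t(18) = 2.101, the 95% half-width would be 0.96 SD. On the same footing, 6 fed active against 8 fed placebo has 2.179 × 0.540 = 1.18 SD, and 6 active against 20 pooled has 2.064 × 0.465 = 0.96 SD. The plan calls for no such intervals; they only show how coarse each reading is.

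**Comparisons in which the meal cancels.**
- One fed dose against another (20, 40, 80, 160 mg): m - m = 0 for a common meal effect, so a dose trend within the fed part is unaffected.
- All active against all placebo in the AE displays: active is 36 fasted and 24 fed, also 0.6/0.4, so 0.4m - 0.4m = 0.

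**The case for a change.** The best case for adding a sentence is that the text states two placebo comparisons, fasted with fed placebo and pooled placebo with every active group, and never says that a fed group should be read against fed placebo. The plan separates meal conditions for dose proportionality (Protocol 7.3.2) and for the QTcF and heart-rate exposure-response models (SAP 7.8.4), so silence in the descriptive tables looks like an oversight. The placebo-versus-placebo check is weak: similar-looking columns would not exclude a meal effect near 1 SD. A sentence would need no new table or programming.

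The carry-over fractions and the weakness of that check stand. The rest supports a reminder at most:

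- The matched columns exist, and the general statement in Protocol 7.3.4 about comparing treatments does not exclude using them.
- Precision counts both ways: the matched fed comparison is coarser than the check being faulted (1.18 against 0.96 SD).
- With m unknown, an instruction to prefer the matched column cannot be justified for any particular parameter.
- A fixed 4:00 limit has no basis in the documents. At 6:00 fed subjects have had breakfast and lunch, fasted subjects only lunch. Leaving AEs out is no firmer, since AE displays also show single-condition dose groups, where a meal effect would not cancel.
- The laboratory part is thin. SAP 7.8.2 compares values with reference ranges, although Protocol 7.3.4 adds differences from baseline, and Protocol 5.2.3 already discloses the non-fasted sample.

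**Conclusion.** No change to the plan. Pooling placebo is a fair trade-off between precision and comparability, and it comes with a planned comparison of its two components. The possible distortion is up to +0.6m for a fed group and -0.4m for a fasted group, and only for a reader who ignores the same-condition column in the same table. No planned estimate, interval, test or table would change. An analyst writing the report can be expected to look at both columns when an early vital-sign or ECG shift appears in a fed group, and to look for a dose trend across the fed groups.

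If the report authors wish, a table footnote may remind readers to consult both the pooled and the same-condition placebo column, without ranking them and without a time limit.

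This rests on the planned 12 + 8 placebo split, a common SD, a baseline taken before breakfast as scheduled (otherwise the carry-over is smaller), and the public text of the SAP, in which Section 9.3 on the ECG models is not available.
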